7.1.4. Weeks 16, 40, and Repeat Visit A

Subjects will return to clinic for these scheduled visits within a \pm 5-day “window.” The following will be completed:

- Adverse event monitoring
- Use of concomitant medications
- Vital signs (blood pressure [supine], temperature and pulse)
- Brief physical and neurologic examination
- Height
- Weight
- C-SSRS – Since Last Visit version
- Receive and count remaining tablets in each returned bottle of investigational product to assess adherence to BID dosing.

A 188-count bottle of study drug to be dispensed is assigned by the computer-based study management system.

7.1.5. Weeks 28, 52, and Repeat Visit B

Subjects will return to clinic for these scheduled visits within a \pm 5-day “window.” The following will be completed:

- Adverse event monitoring
- Use of concomitant medications
- Vital signs (blood pressure [supine], temperature and pulse)
- Brief physical and neurologic examination
- Height

- Weight
- 12-lead resting ECG (5-min supine)
- Clinical laboratory tests (biochemistry, hematology, and urinalysis)
- Collect samples for HbA1c (only if collected at the original Study Day 1 visit or on Re-entry Day 1) and plasma biomarkers
- CDR
- C-SSRS – Since Last Visit version
- Receive and count remaining tablets in each returned bottle of investigational product to assess adherence to BID dosing.

A 188-count bottle of study drug to be dispensed is assigned by the computer-based study management system

7.1.6. End-of-Treatment Visit (EoT) / Early Termination (ET) Visit

Subjects will return to clinic for this scheduled visit within a \pm 5-day “window.” The following will be completed:

- Adverse event monitoring
- Use of concomitant medications
- Vital signs (blood pressure [supine], temperature and pulse)
- Brief physical and neurologic examination
- Height
- Weight
- 12-lead resting ECG (5-min supine)
- Clinical laboratory tests (biochemistry, hematology, and urinalysis)
- Collect samples for HbA1c (only if collected at the original Study Day 1 visit or on Re-entry Day 1) and plasma biomarkers
- CDR (End of Treatment visit only)
- C-SSRS – Since Last Visit version
- Receive and count remaining tablets in each returned bottle of investigational product to assess adherence to BID dosing.

7.1.7. End-of-Study Follow-up Phone Call

The subject and/or study partner will receive a follow-up phone call 7-14 days after the last dose of study drug for adverse event monitoring. If needed, a follow-up clinic visit will be

scheduled.

7.1.8. Unscheduled Visits and Discontinuation due to AEs

For unscheduled visits due to AEs, any assessments conducted will be at the discretion of the Investigator and pertinent to the AE. If a decision is made to discontinue the subject from study drug, the Sponsor will be notified immediately. The subject should be followed and treated by the Investigator until the AE has resolved or stabilized (see Section 10 – Adverse Events). Restarting the subject on study drug will be a mutual decision by the Investigator and the Sponsor. See also Section 9 – Early Discontinuation.

7.1.9. Stopping Criteria

Liver chemistry threshold stopping criteria have been designed to ensure subject safety and to evaluate liver event etiology during administration of study drug. Potential discontinuation of study drug for abnormal liver function tests should be considered by the Investigator in consultation with the designated medical monitor if the study subject meets one or more of the following criteria:

- ALT or AST $\geq 4x$ ULN;
- ALT or AST $\geq 3x$ ULN and total bilirubin $\geq 2x$ ULN;
- ALT or AST $\geq 3x$ ULN if associated with the appearance or worsening of fatigue, nausea, vomiting, right upper quadrant pain or tenderness, fever, rash and/or eosinophilia; or
- ALP elevations, if deemed of liver origin and drug-related as follows:
 - ALP $> 3x$ ULN;
 - ALP $> 2.5x$ ULN and total bilirubin $> 2x$ ULN; or
 - ALP $> 2.5x$ ULN if associated with the appearance or worsening of fatigue, nausea, vomiting, right upper quadrant pain or tenderness, fever, rash and/or eosinophilia.

In the event of discontinuation due to abnormal liver function tests, the subject will be appropriately investigated to determine the potential cause and referred to a physician experienced in the treatment of hepatic disorders.

Study drug should be discontinued if a subject: (1) positively affirms suicidal ideation in response to questions number 4 or 5 in the suicidal ideation section of the C-SSRS, or (2) reports any suicidal behavior or non-suicidal self-injurious behavior since their last visit in response to the C-SSRS Suicidal Behavior questions. The subject should be referred to a psychiatrist or an appropriate health care professional for further evaluation and

management.

Bodyweight loss of ≥ 2 kg from Study Day 1 resulting in a BMI < 18.5 is an additional stopping criterion. (Note: BMI at any specific visit utilizes the height and weight recorded on that day.)

7.2. LABORATORY ASSESSMENTS

7.2.1. *Clinical Laboratory Tests*

The following clinical laboratory tests will be performed on Study Day 1, as well as the Re-entry Day 1 (for select participants), Week 4, Re-entry Week 4, Week 28, Week 52, Repeat Visit B, and End of Treatment/Early Termination Follow-up visits:

- **Biochemistry**: glucose, sodium, potassium, chloride, bicarbonate, calcium, phosphate, blood urea nitrogen (BUN), total bilirubin, creatinine, albumin, globulin, total protein, uric acid, alkaline phosphatase (ALP), alanine transaminase (ALT), aspartate transaminase (AST), gamma glutamyl transpeptidase (GGT), lactate dehydrogenase (LDH). For new participants, HbA1c will be analyzed on Day 1, Week 28, Week 52, Repeat Visit B, and EoT/ET. For active participants HbA1c will be analyzed at Week 28, Week 52, Repeat Visit B, and EoT/ET only if HbA1c was collected and analyzed on Study Day 1. For re-entering participants, HbA1c is analyzed at Re-entry Day 1, Repeat Visit B, and EoT/ET.
- **Hematology**: white blood cell (WBC) count with differential, red blood cell (RBC) count, hemoglobin, hematocrit, platelet count.
- **Urinalysis**: color, specific gravity, pH, protein, glucose, ketones, occult blood, nitrites and leukocyte esterase. A “reflex” microscopic examination will be performed if protein, occult blood, nitrites or leukocyte esterase is present on the basic analysis.

7.2.2. *Preparation of Samples for Plasma Biomarkers*

At each blood collection for plasma biomarkers, blood samples will be drawn into a Vacutainer® tube (10 mL per tube) containing K2EDTA. The tubes will be placed immediately on ice upon collection. Following the instructions within the Laboratory Manual, the plasma samples will be centrifuged, frozen (within 30 minutes of centrifuging), and shipped to the central laboratory.

8. COGNITIVE ASSESSMENT

8.1. CLINICAL DEMENTIA RATING SCALE

Washington University's CDR² characterizes six domains of cognitive and functional

performance applicable to AD and related dementias: memory, orientation, judgment and problem solving, community affairs, home and hobbies, and personal care. The study partner is interviewed first by a qualified rater who assesses all six domains in the absence of the study subject. The subject is then interviewed by the same rater in the absence of the study partner. A CDR global score can be calculated by accessing Washington University's online algorithm ([CDR® Calculator | National Alzheimer's Coordinating Center \(naccdata.org\)](https://naccdata.org/)) where 0 = no dementia, and scores of 0.5, 1, 2, or 3 = questionable, mild, moderate, or severe dementia, respectively. The sum of boxes³ can also be calculated by summing the six individual domain scores. This detailed quantitative general index may provide more information than the CDR global score in patients with mild dementia.

9. SAFETY ASSESSMENTS

9.1. COLUMBIA-SUICIDE SEVERITY RATING SCALE

The C-SSRS⁴ is an assessment tool used to assess the lifetime suicidality of a subject (C-SSRS at baseline) as well as any new instances of suicidality (C-SSRS Since Last Visit).

10. EARLY DISCONTINUATION

Subjects may choose to discontinue study drug or study participation at any time, for any reason, and without prejudice. Moreover, a subject may be withdrawn at any time at the discretion of the Investigator or Sponsor for safety, behavioral or administrative reasons. Discontinued subjects should be followed according to medical practice standards, and the outcome documented. Follow-up is required if the subject is discontinued due to an adverse event (AE). Any comments (spontaneous or elicited) or complaints made by the subject and the reason for termination and the date of stopping the drug must be recorded in the Case Report Form (CRF) and source documents.

The following must be completed and documented in the CRFs and source documents for all subjects who discontinue the study early:

- The reason for early study discontinuation. If the subject is withdrawn for more than one reason, each reason should be documented in the source documents and the most clinically relevant reason should be entered on the CRF.
- Vital signs (blood pressure, temperature, and pulse), brief physical and neurologic examination, height, weight, clinical laboratory tests, collection of HbA1c (if collected on Study Day 1 or Re-entry Day 1), plasma biomarkers, ECG, use of concomitant medications, and adverse events should be obtained at discharge prior to release.
- C-SSRS (as detailed in Section 7.1.6 – Early Termination Visit), if not performed within the last 30 days.

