7.1. EVALUATIONS BY VISIT

Follow-up visits can be scheduled +/- five (5) days from the targeted Study Visit date.

7.1.1. *Study Day 1 (Dosing Initiation)*

The clinical and laboratory assessments performed at the Week 76 (PTI-125-06) or Week 52 (PTI-125-07) End-of-Treatment visit will serve as the baseline (Study Day 1) for this open-label extension study. Subjects will come to the clinic in the morning whenever possible. Prior to dosing, the following will be completed:

- Informed Consent
- Height (to facilitate BMI calculation)
- Collect samples for HbA1c and plasma biomarkers
- Review of I/E criteria following all Study Day 1 assessments and prior to dosing.

From the Week 76 or Week 52 End-of-Treatment visit (PTI-125-06 or PTI-125-07, respectively) in the phase 3 study in which the subject participated:

- Review of concomitant medications
- Adverse Event Monitoring
- C-SSRS – Since Last Visit version
- Vital signs (blood pressure [supine], temperature, pulse)
- Weight
- Brief physical and neurologic examination (Note: the brief physical and neurologic examination performed on Study Day 1 and at all subsequent visits will include an assessment of the following: general appearance; cardiovascular, pulmonary, and abdominal examination, as well as an examination of any other system in response to subject-reported symptoms; cranial nerves [II-XII], tone, power, deep tendon reflexes, coordination and gait)

- Clinical laboratory tests (biochemistry, hematology, and urinalysis)
- 12-lead resting ECG (5-min supine)
- CDR

If the Study Day 1 (baseline) visit does not coincide with the Week 76 or Week 52 End-of-Treatment visit for the double-blind study (PTI-125-06 or PTI-125-07, respectively), the Investigator should confer with the Medical Monitor to determine whether selected assessments may need to be repeated.

Once all Study Day 1 procedures and assessments have been completed, the 70-count bottle of study drug to be dispensed is assigned by the computer-based study management system.

Subjects will be administered one (1) tablet of study drug at the clinic at least 4 hours after any prior dose and at least 1 hour before departure. The subject will be discharged with their supply of study drug. The study partner will be instructed to administer study drug twice daily with or without food. The study partner should be advised that a dose can be up to 4 hours late, but, if a dose is missed, the next dose should NOT be doubled.

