# 3.7. Schedule of Events

**Table 1: Schedule of Events** 

[figure not shown]
Procedures	Baseline Visit (Study Day 1)	Week 4	Week 16	Week 28	Week 40	Week 52 ET/ED 	Week 53 to 54
Informed Consent	X						
I/E Criteria	X						
Adverse Events	X	X	X	X	X	X	X
Concomitant Meds	X	X	X	X	X	X	
Vital signs	X	X	X	X	X	X	
Brief Physical Examination	X	X	X	X	X	X	
Brief Neurologic Examination	X	X	X	X	X	X	
Height	X						
Weight	X	X	X	X	X	X	
Resting ECG	X	X		X		X	
Biochemistry, Hematology, Urinalysis	X	X		X		X	
HbA1c 	X			X 		X 	
C-SSRS 	X	X	X	X	X	X	
Drug Dispensation	$X^2$	X	X	X	X		
Drug Accountability		X	X	X	X	X	
End of Study Follow- up Phone Call							X

- 1. On Study Day 1, as well as all remaining visits, the 'C-SSRS Since Last Visit' version will be administered.
- 2. The first dose of study drug is administered at the clinic to all subjects on Study Day 1 at least four hours after any prior dose and at least one hour before departure.
- 3. HbA1c collection will begin upon receipt of required supplies.
- 4. Week 28 and Week 52 HbA1c should only be collected in subjects with a Day 1 HbA1c.

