# 10. Changes from Planned Analyses

Due to the early sponsor termination of PTI-125-10, the following analyses will no longer be tabulated/listed:

- Mean change in clinical laboratory values from baseline to Weeks 4, 28 and 52
- Mean change in vital signs (blood pressure [supine], temperature, pulse rate) from baseline to Weeks 4, 16, 28, 40, and 52
- Mean change in body weight from baseline to Weeks 4, 16, 28, 40, and 52

- Shifts in physical exam (PE) findings from baseline to Weeks 4, 16, 28, 40, and 52
- Shifts in neurological exam (NE) findings from baseline to Week 4, 16, 28, 40, and 52
- Mean change in ECG parameters from baseline to Weeks 4, 28, and 52
- Concomitant medications/treatments usage
- Shifts in the C-SSRS from baseline to Weeks 4, 16, 28, 40, and 52.
- Shifts in HbA1c values from baseline to Weeks 28 and Week 52. The analysis is done separately among subjects who were previously on placebo and simufilam in PTI-125-06 and PTI-125-07 phase 3 studies.

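### Section 10 lets sites skip the C-SSRS at early discontinuation if one was done within 30 days, while Section 7.1.6 and both schedules require it unconditionally

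*Protocol*

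**What the plan says.** Protocol Section 10 introduces its exit requirements with "The following must be completed and documented in the CRFs and source documents for all subjects who discontinue the study early". The last item is "C-SSRS (as detailed in Section 7.1.6 – Early Termination Visit), if not performed within the last 30 days". In the same list, vital signs, the physical and neurologic examination, laboratory tests and the ECG carry no recency condition.

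Section 7.1.6, the list for the combined End-of-Treatment/Early Termination visit, has only "C-SSRS – Since Last Visit version". Two neighbouring items do carry conditions: HbA1c depends on an earlier sample, and the CDR is limited to End of Treatment. Appendices B and C both mark the C-SSRS in the EoT/Early Term column, and their footnotes give no exemption. The SAP's Table 1, which follows a 52-week schedule, also marks it at ET/ED; its footnote applies the since-last-visit version "On Study Day 1, as well as all remaining visits".

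The timing of the preceding form matters too. Under Section 7.1.1 the Study Day 1 C-SSRS is the one from the parent study's End-of-Treatment visit. "If the Study Day 1 (baseline) visit does not coincide with the Week 76 or Week 52 End-of-Treatment visit", the investigator discusses with the Medical Monitor whether to repeat assessments. Under Section 7.1.2 the Re-entry Day 1 form is completed before dosing.

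After exit, Section 7.1.7 provides a call "7-14 days after the last dose of study drug for adverse event monitoring". Section 7.1.9 makes certain C-SSRS responses a reason to stop drug and adds: "The subject should be referred to a psychiatrist or an appropriate health care professional".

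**The concern.** The same visit has two rules, and a site can follow either in good faith. Section 10 permits the omission and does not order it, so a site working from Section 7.1.6 or the schedules would still complete the form.

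The exit form is the one that cannot be made up. If a since-last-visit form is missed mid-study, the next one covers the gap; after exit there is no next one. The participant is in any case being examined, having blood drawn and having an ECG, yet only the suicidality form is excused on grounds of recency. Section 10 also allows withdrawal for safety or behavioural reasons, so some of these participants leave in circumstances where the questions matter.

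If the form is skipped, new ideation or behaviour in the last interval has to surface through adverse event reporting, which Section 11.1 bases on a non-specific question, or through the phone call. What is lost is the structured questioning that leads to the psychiatric referral in Section 7.1.9.

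**Working it through.** The plan gives no figure of its own here, so the check is a comparison of texts followed by interval arithmetic.

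**Which rule applies.** Section 10 makes the form conditional on 30 days. Section 7.1.6, Appendix B, Appendix C and the SAP's Table 1 do not. The 30-day exemption appears nowhere else in the current protocol. Section 7.1.6 states conditions where it intends them (HbA1c, CDR), so its silence on the C-SSRS reads as a requirement.

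**Inputs.**
- Waiver: 30 days (Section 10).
- New participants: visits at Weeks 4, 16, 28, 40 and 52, that is, 28 days and then four intervals of 84 days; 28 + 4 × 84 = 364 days (Appendix B).
- Re-entry participants: Repeat Visit A at 12 weeks, with a Week 4 visit only if Week 52 was more than 60 days before re-entry (Appendix C).
- Visit window: ±5 days (Section 7.1).
- Assumptions, not in the documents: visits on target; withdrawal equally likely on any day; g = days from the parent-study form to Study Day 1.

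**Longest uncovered time at exit.** Under Section 10, 30 days. Under Section 7.1.6 and the schedules, 0 days.

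**Share of withdrawal days on which the form may be omitted.**

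| Situation | Calculation | Share |
|---|---|---|
| Any 12-week interval | 30/84 | 36% |
| Same, interval of 94 or 74 days under the windows | 30/94; 30/74 | 32%; 41% |
| New, 52 weeks, g = 0 | (28 + 4 × 30)/364 = 148/364 | 41% |
| New, 52 weeks, g = 14 | (16 + 4 × 30)/364 = 136/364 | 37% |
| New, 52 weeks, g ≥ 30 | (0 + 4 × 30)/364 = 120/364 | 33% |
| Re-entry, first 12 weeks, gap > 60 days | (28 + 30)/84 = 58/84 | 69% |
| Re-entry, first 12 weeks, gap ≤ 60 days | 30/84 | 36% |

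For new participants the first term is min(28, max(0, 30 − g)). The re-entry rows use a 12-week horizon and should not be set directly against the 52-week rows. Over 52 weeks, re-entry with a gap above 60 days gives (28 + 30 + 30 + 30 + 30 + 28)/364 = 176/364 = 48%.

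**The first interval.** The last day before an on-target Week 4 visit is Day 1 + 27. The parent-study form is then 27 + g days old, which is 30 or less when g ≤ 3. So if the parent form was done within about 3 days of Study Day 1, any withdrawal before Week 4 can go without a C-SSRS after the first open-label dose. For someone who was on placebo, that means none on simufilam. Someone who was on simufilam already has forms on drug. A re-entry participant who leaves before the next visit and within 30 days can have no form after the restart dose, but has forms on drug through Week 52.

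**The case against.** The texts can be reconciled. Section 7.1.6 lists a combined visit, while Section 10 deals only with early discontinuation and qualifies the list it cites. On that reading the defect is a missing cross-reference, and the 30-day rule is a choice that no document shows to be inadequate. This has some force, but Section 7.1.6 and the footnotes would then need correcting, so the text needs a change either way.

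The other safeguards go beyond the exit adverse event question and the call. Section 10 requires follow-up to medical practice standards and a record of any comments or complaints. Follow-up is mandatory after withdrawal for an adverse event. The call can lead to a clinic visit, and serious events within 30 days of drug are reportable within 24 hours. All of this stands, and it narrows the gap. None of it is structured suicidality questioning.

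Stopping drug, the main action in Section 7.1.9, is moot for someone already leaving. That is right; referral is not moot. The uncovered time is capped at 30 days and, under the even-spread assumption, averages about 15 days among exits within the waiver in a 12-week interval.

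The percentages are soft. Even spread of withdrawals is unsupported, and a participant who stops at a scheduled visit has a form that same day and loses nothing. How often sites use the waiver is unknown. The case of no form on simufilam needs a former-placebo participant, a small g, an exit before Week 4 and a site that uses the waiver.

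Finally, the SAP records that the sponsor ended the study early, so a protocol edit may now protect few participants in it.

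**Conclusion.** The concern holds. The current protocol gives conflicting rules for the C-SSRS at early discontinuation, and the one in Section 10 permits an exit with up to 30 days, or all post-dose time for some who leave before Week 4, without a structured suicidality assessment. The calendar shares describe when omission is allowed and rest on on-target visits and evenly spread withdrawals; no rate of missed forms or missed events can be derived from the documents.

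The effect is on individual safety monitoring. No planned output changes: protocol Section 12.2 names no C-SSRS analysis, and SAP Section 10 lists "Shifts in the C-SSRS from baseline to Weeks 4, 16, 28, 40, and 52" among the analyses dropped. Confidence in the conflict of texts is high. The safety consequence is plausible but of unknown frequency. The point should be fixed, but it does not threaten the study's conclusions.

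**What to change.** Delete the 30-day condition from the C-SSRS item in Section 10, so that it agrees with Section 7.1.6 and Appendices B and C and every early leaver has a form covering the time from the last one to exit. Tell sites by memo.

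The cost is one clause, one memo and a short interview for some early leavers; the form is already scheduled at that visit. If the sponsor does intend the waiver, it should be written into Section 7.1.6 and the footnotes of both appendices, but that would leave the uncovered interval in place. Given the early termination, the edit matters for any exits still to come and for any protocol that reuses this text.

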11. ADVERSE EVENTS/SERIOUS ADVERSE EVENTS

11.1. ADVERSE EVENTS – DEFINITION

An Adverse Event (AE) is any undesirable event that occurs to a subject during a study, whether or not that event is considered study drug-related. Monitoring for AEs will start at dosing. Examples include:

- Any treatment-emergent signs and symptoms (events that are marked by a change from the subject's baseline/entry status [e.g., an increase in severity or frequency of pre-existing abnormality or disorder])
- All reactions from study drug, an overdose, abuse of drug, withdrawal phenomena, sensitivity or toxicity to study drug
- Apparently unrelated illnesses
- Injury or accidents (Note: if a medical condition is known to have caused the injury or accident, the medical condition and the accident should be reported as two separate medical events [e.g., for a fall secondary to dizziness, both "dizziness" and "fall" should be recorded separately])
- Extensions or exacerbations of symptoms, subjective subject-reported events, new clinically significant abnormalities in clinical laboratory, physiological testing or physical examination

All AEs, whether or not related to the study drug, must be fully and completely documented on the AE page of the CRF and in the subject's clinical chart.

In the event that a subject is withdrawn from the study because of an AE, it must be recorded on the CRF as such. The subject should be followed and treated by the Investigator until the abnormal parameter or symptom has resolved or stabilized.

The Investigator must report all directly observed AEs and all spontaneously reported AEs. The Investigator will ask the subject a non-specific question (e.g., "Have you noticed anything different since your dose of the study medication?") to assess whether any AEs have been experienced since the last assessment. AEs will be identified and documented in the Electronic Data Capture (EDC) system in appropriate medical terminology. The severity and the relationship to the study drug will be determined and reported in EDC (see below).

